The undersigned confirm that the following protocol has been agreed and approved by the Sponsor and that the Chief Investigator agrees to conduct the study in compliance with this approved protocol and will adhere to the principles of GCP, the Sponsor SOPs, and any other applicable regulatory requirements as may be amended from time to time.

[name]		
Chief Investigator	Signature:	Date:
[name]		
Individual Responsible for Statistical Review	Signature:	Date:
[name]		
Co-Investigator	Signature:	Date:

LIST OF ABBREVIATIONS

AE	Adverse Event
AUROC	Area Under the Receiver Operating Characteristic Curve
BI-RADS	Breast Imaging and Reporting Data System
BPE	Background Parenchymal Enhancement
CE-DBT	Contrast-Enhanced Digital Breast Tomosynthesis
CESM	Contrast-Enhanced Spectral Mammography
СІ	Chief Investigator
CNORIS	Clinical Negligence and Other Risks Scheme
CRF	Case Report Form
DBT	Digital Breast Tomosynthesis
DCE-MRI	Dynamic Contrast-Enhanced Magnetic Resonance Imaging
DM	Digital Mammography
DMC	Data Monitoring Committee
DMS	Data Management System
GCP	Good Clinical Practice
GP	General Practitioner
ICF	Informed Consent Form
HRA	Health Research Authority
HRT	Hormone Replacement Therapy
IF	Incidental Findings
MDT	Multidisciplinary Team
MRI	Magnetic Resonance Imaging
NCTIMP	Non-Clinical Trials of Investigational Medicinal Products
NHS	National Health Service
OCP	Oral Contraceptive Pill
РІ	Principal Investigator
PIS	Patient Information Sheet
REC	Research Ethics Committee
ROC	Receiver Operator Characteristic
SAE	Serious Adverse Event
SOP	Standard Operating Procedures
SMG	Study Management Group
TASC	Tayside Medical Science Centre
US	Ultrasound
VAS	Visual Analogue Scale

SUMMARY/SYNOPSIS

Study Title	CONT rast Enhanced breaSt Tomosynthesis (CONTEST) in patients suspected of having breast cancer: a prospective comparison with digital mammography and breast MRI								
Study Design	Prospective non-randomised paired comparison of CE-DBT and breast MRI								
Study Population	Consented symptomatic women attending the Breast Clinic with clinical suspicion of breast cancer								
Sample Size	200 women								
Planned Study Period	3 years								
Clinical Phase Duration	2 years								
Follow-up Phase Duration	None								
Primary	Objectives Outcome Measures								
	To assess the incremental diagnostic performance of CE- DBT over DM in the diagnosis of breast cancerSensitivity of CE-DBT comp with DM using surgical pathe as the gold standard								
Secondary	Objectives	Outcome Measures							
	To assess the accuracy of local staging of breast cancer with CE- DBT compared with DM, US and MRI Correlation of tumour size measurements and identifica multifocality with CE-DBT compared to MRI, using sure pathology as the gold standa								
Inclusion Criteria	Women aged 18 to 70 years old with clinical suspicion of breast cancer								
Exclusion Criteria	Women unable to undergo CE-DBT								
	Women unable to undergo breast MRI								
	Women with locally advanced cancer who are likely to receive neoadjuvant chemotherapy								
	Women with severe comorbidities precluding surgical treatment								

1 INTRODUCTION

It is well established that digital mammography (DM) has limitations in the diagnosis of breast cancer in both symptomatic and screening populations¹. This is largely attributable to obscuration of masses by overlapping normal fibroglandular parenchyma, particularly in women with dense breasts, seen in up to 40% of Scottish women. Even with state-of-the-art DM, sensitivity in the dense breast can be under 60%². In the symptomatic clinic setting, diagnostic uncertainty about the presence and extent of breast cancer can persist, even after complementary breast ultrasound. This can necessitate subsequent supplemental tests such as breast magnetic resonance imaging (MRI) to allow treatment planning.

The shortfalls of DM have been partly addressed by development of two novel mammographic techniques.

Digital breast tomosynthesis (DBT) is a quasi-3D mammographic technique, which improves visibility of malignant structural features, particularly spiculation. Its ability to resolve composite opacities also increases specificity compared with DM. Published studies show increased cancer detection rates of 20-30%, with a concurrent reduction in recall rates in the screening setting³. Research by our group and others has established that DBT can accurately characterise indeterminate mammographic abnormalities detected at screening⁴.

Contrast-enhanced spectral mammography (CESM) is a 2D mammographic technique yielding functional information on the vascularity of breast lesions through dual energy subtraction. It enables the neovascularisation of malignant tumours to be detected. The diagnostic accuracy of CESM in the literature is better than DM and comparable to MRI, with sensitivities over 90%⁵⁻⁷. This is despite the fact that timings of image acquisition after contrast medium administration are quite different between CESM and MRI.

Spiculation, the feature highlighted by DBT, is most frequently seen in low grade, relatively indolent breast cancers⁸. Conversely, the pathological process underpinning visualisation of tumours at CESM, neoangiogenesis, is more pronounced in aggressive high grade cancers, which may appear paradoxically benign at DM and DBT⁹.

CE-DBT is a new imaging modality combining the structural and functional information from DBT and CESM (manufactured by Hologic^R and CE marked; Selenia Dimensions with *i-View* software) respectively into a single, short examination, depicting the entire biological spectrum of breast cancer. It can be performed quickly and economically in the outpatient breast clinic, so could provide a major step forward in prompt one-stop characterisation of breast lesions without recourse to breast MRI. Though MRI is the gold standard in breast cancer detection and local staging, it is difficult to access in a timely fashion, expensive and time consuming. In many patients, it is either contraindicated (e.g. in patients with pacemakers), not tolerated, or - increasingly - not possible because of body habitus. CE-DBT could therefore represent an effective, cost-efficient alternative to MRI.

2 BACKGROUND & RATIONALE

Increasing pressure on diagnostic services in Scotland poses challenges to timely diagnosis and local staging of breast cancer. Between 20 and 40% of women in Scotland have dense breast tissue, rendering assessment with conventional imaging problematical. The need for supplemental tests such as MRI incurs substantial delays in treatment planning, risking additional anxiety and distress for our patients, and increased costs. CE-DBT could obviate the need for further tests in many patients. Breast cancer charities are reluctant to fund studies of novel imaging tests requiring expenditure on equipment/software, and a study such as the one proposed here is essential before a multicentre study with full health economic evaluation can be carried out.

Demonstration of superior accuracy of CE-DBT over DM would have profound implications for the diagnostic work-up of women suspected of having breast cancer, especially where DM has limitations (invasive lobular cancers, mammographically occult cancers, imaging and/or clinical size discrepancies). The ability to diagnose more reliably the entire spectrum of breast cancers

in a single examination at the initial clinic visit, would greatly speed up the diagnostic pathway for many patients. Since mammography is generally performed prior to ultrasound (US), CE-DBT could prompt immediate ultrasonographic assessment of all areas of potential disease in both breasts, ensuring timely, thorough diagnostic work-up without recourse to further tests. This would reduce patient anxiety, inconvenience, and service costs, while speeding up treatment planning.

As CE-DBT is an entirely novel technique, no pilot data are available. However, one small study from elsewhere used a prototype CE-DBT unit that is not currently available¹⁰. In this study of only 36 invasive cancers, there was no significant difference in the diagnostic performances of MRI, CESM or CE-DBT, but even with such small numbers, all three techniques significantly outperformed 2D DM.

There is, however, good evidence from the literature on the incremental diagnostic accuracy of DBT and CESM over DM. CESM increases the sensitivity of DM by up to 20%^{5,6,11,12} and in a recent meta-analysis had an overall sensitivity of 98%¹³. In the screening setting, DBT results in incremental breast cancer detection rates of 3.9 per 1000 screens in women with dense breasts, with lower recall rates (23/1000 screens)¹⁴. A comparative study of DM, DBT and MRI showed that both the latter are more accurate than DM in lesion sizing and evaluation of tumour extent¹⁵.

Thus, the key research questions are:

a) Does CE-DBT improve upon the diagnostic accuracy of DM in women presenting with symptoms suspicious of breast cancer? (the primary objective)

b) Is local staging (lesion size, focality assessment, prediction of invasive and in situ disease) with CE-DBT sufficiently accurate to obviate the need for breast MRI? (the secondary objective).

Additional research questions include:

c) Whether patient-related factors such as mammographic density and age influence the performance of CE-DBT

d) Does background parenchymal enhancement (BPE) occur as frequently as in breast MRI and does it impair interpretation of CE-DBT, as it can with MRI¹⁶?

e) Identification of any histological features affecting the comparative accuracy of CE-DBT compared with breast MRI.

3 STUDY OBJECTIVES & OUTCOMES

The aim of this study is to evaluate the performance of CE-DBT in the identification and local staging of symptomatic breast cancer. The primary objective is to determine the incremental increase in sensitivity of CE-DBT over DM alone in women with symptoms/signs suspicious for breast cancer, the latter currently being standard of care. This will be assessed through comparison with post-surgical pathology in all women with biopsy-proven breast cancer treated with primary surgery.

The second objective is to assess the accuracy of local cancer staging with CE-DBT regarding extent and the presence/ absence of multifocality. All patients with biopsy-proven breast cancer will undergo breast MRI, since this is the current imaging gold standard and a head to head comparison of CE-DBT and MRI against surgical pathology will be made.

Thirdly, planned subset analysis will explore the influence of age, breast density, and BPE on the diagnostic performance of CE-DBT. In order to address this, participants will undergo CESM of the index breast at two time points to enable semi-quantitative kinetic analysis of lesional and background contrast enhancement in comparison to breast MRI to determine whether this affects diagnostic performance.

Finally the study will explore the accuracy of CE-DBT in the subset of women who would normally receive pre-operative breast MRI as standard of care and will aim to identify clinicopathological features influencing the accuracy of CE-DBT in a planned subset analysis.

Table 1: Primary Objectives and Outcome Measures

Primary Objective:	Outcome Measure:	Timepoint of outcome measured
Diagnostic performance of CE- DBT in the diagnosis of breast cancer	Incremental sensitivity of CE-DBT versus DM, compared to gold- standard surgical pathology	Final 6 months of study

Table 2: Secondary Objectives and Outcome Measures

Secondary Objective:	Outcome Measure:	Timepoint of outcome measured
Assessment of comparative accuracy of CE-DBT and MRI in local staging of breast cancer	Variance between CE-DBT, MRI and pathology	Final 6 months of study
Comparison of specificity of CE- DBT versus breast MRI at breast level	Number of false positive examinations (score 3 or above) with each imaging modality	Final 6 months of study
Comparative accuracy of CE- DBT and MRI in women who would normally have preoperative MRI	Subgroup analysis (invasive lobular cancers, clinical-imaging size discrepancy, mammographically occult cancer): AUROC curve analysis of diagnostic accuracy	Final 6 months of study
Evaluation of clinicopathological factors affecting performance of CE-DBT	Subgroup analysis by: age, breast density, BPE, histology. AUROC analysis	Final 6 months of study

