4.10 NUMBER OF PARTICIPANTS

The study aims to recruit 200 women with clinical suspicion of breast cancer. Analysis of data from the symptomatic clinics at Ninewells Breast Unit (NHS Tayside) shows that around 75% of these (150) will subsequently prove to have breast cancer on biopsy. With a conservative estimated consent rate of 50% and screen failure rate of between 10-20% this equates to a recruitment rate of one to two patients per week over 2 years, the anticipated recruitment period.

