5.5 WITHDRAWAL PROCEDURES

- Participants will be withdrawn if the CE-DBT examination is not completed.
- Any women declining needle biopsy will be withdrawn from the study because it will not be possible to determine a definitive diagnosis.
- Participants:
 - Who, after a diagnosis of breast cancer, prove unsuitable for initial surgical treatment (severe co-morbidities), or
 - \circ Who decline surgery, or
 - Where initial surgical treatment does not occur (e.g. neoadjuvant chemotherapy to allow breast conservation)

Will be excluded from further analysis because full pathological-radiological correlation will not be possible.

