7.2 PROPOSED ANALYSES

Formal analysis will take place in the last six months of the study after recruitment is complete.

Analysis will require 4 months of expert statistical input. [name], Professor of Bioinformatics at Nottingham Trent University, has great expertise in cancer systems biology, identification of biomarkers, development of prognostic indices and application of statistics to medical diagnostics. At the start of the study he will oversee design of the case report forms to ensure that all relevant data fields are captured and he will carry out data analysis in the final quarter of the study.

Analysis:

1) Comparing incremental sensitivity and specificity between DM and CE-DBT:

True and false positive and negative rates in comparison with histopathology will be computed for each modality, at individual lesion level. BIRADS 1&2 will be considered negative and 3-5, positive. Shifts in BIRADS classifications between modalities will be analysed, to identify differences in diagnostic certainty. Receiver Operator Characteristic curves will be utilised as a standard for evaluation of classification performance.

2) Comparing performance between CE-DBT and MRI for local staging:

Malignant lesions classified as unifocal: measurement accuracy will be compared (whole tumour diameter variance in mm from histological size). Diagnostic accuracy for additional lesions (not detected clinically or seen at initial diagnostic DM) will be compared between CE-DBT and MRI using the methods described in #1.

3) The analyses described above will be applied to explore variations in differential performance between CE-DBT and MRI:

- a) by breast density
- b) by age
- c) by levels of BPE
- d) by tumour subtype (invasive lobular versus invasive ductal carcinomas)

We will explore enhancement intensity and temporal patterns of enhancement according to histopathological tumour type and grade.

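### Entry to the primary sensitivity analysis depends on a positive needle biopsy although surgical pathology is the gold standard, so a woman whose only cancer is proven at excision is left out

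*Protocol*

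**What the plan says.** Table 1 in Section 3 gives the primary outcome as "Incremental sensitivity of CE-DBT versus DM, compared to gold- standard surgical pathology". The text of the same section says how it will be assessed: "comparison with post-surgical pathology in all women with biopsy-proven breast cancer treated with primary surgery". The reference test is therefore the surgical specimen, while admission to the set needs a positive needle biopsy followed by primary surgery.

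Other sections also treat needle biopsy as the test that decides who has cancer. Section 4.10 expects about 75% of the 200 women to be those who "will subsequently prove to have breast cancer on biopsy". Section 5.5 states: "Any women declining needle biopsy will be withdrawn from the study because it will not be possible to determine a definitive diagnosis".

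Section 7.2 uses a wider term: "True and false positive and negative rates in comparison with histopathology will be computed for each modality, at individual lesion level". It sets the cut-off, "BIRADS 1&2 will be considered negative and 3-5, positive", but does not say whether the needle or the surgical result decides when they differ.

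Section 4.2 has biopsy directed by clinical and CE-DBT findings, and ultrasound performed in the light of CE-DBT. Section 4.4 gives study MRI to women with biopsy-proven cancer. Section 4.1 provides for no follow-up once the study imaging is complete.

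**The concern.** Every participant enters with strong clinical or ultrasound suspicion (Section 4.11). A surgical excision after a benign or equivocal needle biopsy is therefore plausible, although the protocol does not describe that pathway. If the excision shows cancer, the protocol's own gold standard calls it cancer, but the Section 3 rule leaves the woman out.

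Section 5.5 has the same difficulty. It treats refusal of needle biopsy as making a diagnosis impossible, yet surgery, if it took place, would supply the reference result. Section 7.3 reasons the other way for MRI: a woman who cannot tolerate it may stay in, because CE-DBT can still be compared with surgical pathology.

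At stake is a denominator chosen by a test other than the reference standard, and one that is partly steered by the index test. If the omitted cancers differ in how well DM and CE-DBT show them, the estimated sensitivities and their difference shift. With no follow-up, nothing later in the study would reveal this.

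**Working it through.** **The protocol's own count.** 0.75 × 200 = 150 cancers, defined on biopsy (Section 4.10), reproduces exactly. The figure of 120 in Section 7.1 cannot be reproduced, because alpha, sidedness, power and discordance are not stated there. This point does not depend on it.

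**How a woman is classified, rule by rule.**
- Benign or equivocal needle biopsy, cancer on excision: cancer by Table 1; outside the set by the Section 3 text; undetermined in Section 7.2.
- Needle biopsy declined, cancer on surgical specimen: cancer by Table 1; withdrawn by Section 5.5.
- Extra focus found only at surgery in a woman with another biopsy-proven cancer: she is in the set, and Section 7.2 works per lesion, so the focus still counts.

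The loss is therefore of whole women whose sole cancer is proven at surgery, not of every lesion first seen at surgery.

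**Size, by assumption.** The documents give no share for such women. Take 150 biopsy-proven cancers, DM sensitivity 70% (Section 7.1) and CE-DBT 80% (the 10% increase in Section 7.1, read as points). For simplicity count one lesion per woman. If a share u of all cancers is proven only at surgery, the number added is k = 150u/(1 − u):
- u = 2%: k ≈ 3, denominator 153
- u = 5%: k ≈ 8, denominator 158
- u = 10%: k ≈ 17, denominator 167

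Let DM detect a fraction d of the added cancers and CE-DBT a fraction c. The difference becomes (150 × 0.10 + k(c − d)) / (150 + k) = (15 + k(c − d)) / (150 + k).

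| d, c in the added cancers | u = 2% | u = 5% | u = 10% |
|---|---|---|---|
| 70%, 80% (same as the rest) | 15.3/153 = 10.0 | 15.8/158 = 10.0 | 16.7/167 = 10.0 |
| 50%, 50% | 15/153 = 9.8 | 15/158 = 9.5 | 15/167 = 9.0 |
| 35%, 80% | 16.35/153 = 10.7 | 18.6/158 = 11.8 | 22.65/167 = 13.6 |
| 0%, 100% (extreme) | 18/153 = 11.8 | 23/158 = 14.6 | 32/167 = 19.2 |

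The difference moves only when c − d departs from 10 points, and it can move either way.

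**Scale.** The standard error of a paired 10-point difference in 150 cancers is √((ψ − 0.10²)/150), where ψ is the discordant proportion. At the minimum possible ψ = 10% it is √(0.09/150) = 2.4 points. At an assumed 15% it is √(0.14/150) = 3.1 points. All shifts at u = 2% (−0.2 to +1.8 points) are below one standard error. Larger shifts need a high share together with a very uneven detection pattern.

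**The case against.** The strongest reply is that this is a mismatch of wording. The restriction to operated, biopsy-proven cancers serves a stated purpose, full radiological-pathological correlation, and the study calls itself exploratory. Biopsy follows clinical and ultrasound findings as well as CE-DBT, so selection does not rest on the index test alone. No section describes surgery in a woman who declined biopsy. No effect size can be derived from the documents. Where CE-DBT is better than DM in the omitted cancers by more than 10 points, leaving them out understates the gain and so is conservative. All of this stands, and it keeps the point small. It does not remove the conflict between the Section 3 population, the Section 5.5 rule and the named gold standard.

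Two stronger readings are tempting, and the documents support neither.

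- A reader might infer that cancers proven at surgery will be counted as false positives and so depress specificity. Section 7.2 refers to histopathology, which can include the excision, and Section 6.1 lists surgical pathology among the data collected. No rule labels these women cancer-free. The specificity outcome in Table 2, "Number of false positive examinations (score 3 or above) with each imaging modality", compares CE-DBT with MRI, and study MRI goes only to biopsy-proven cancers, so without an MRI these women cannot enter it as a pair. What remains is that the deciding result for the DM versus CE-DBT specificity is left open. No specificity loss can be calculated from that.
- A reader might infer that both sensitivities are overstated because the lost cancers were the hardest to find. That is not shown. A lesion can be plain on imaging and still be missed by the needle.

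**Conclusion.** The point holds in a limited form. Followed literally, Section 3 omits a woman whose only cancer is proven at excision, and Section 5.5 withdraws a woman without needle biopsy even if the gold standard becomes available. Section 7.2 does not repair either rule. The selection is partly linked to the index test.

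The effect on the CE-DBT minus DM difference is probably small and its direction is unknown. It is nil if these cancers are detected at the same rates as the others. Under an assumed share of 2% to 10%, the difference ranges from 9.0 to 19.2 points, and the upper end needs the extreme pattern at the highest share. The share and the detection rates in these women are assumptions. This is a cheap improvement, not a threat to the primary result.

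**What to change.** 1. In Sections 3 and 7.2, use one definition of cancer status: malignancy on final histology, meaning the surgical specimen where there is one and the needle biopsy otherwise. Add that a cancer wholly removed at biopsy, with no residual tumour in the specimen, still counts as cancer.
2. In Section 6.1, record excision histology for every participant who has surgery. The text there now describes postoperative histology directly after the sentence on cancer cases.
3. In Section 5.5, exclude a woman without needle biopsy from the analysis only if no surgical histology is obtained. The other exclusions in that section are untouched by this point.
4. State that women brought in this way enter the CE-DBT versus DM comparison only.

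The cost is a few sentences and a little more data collection. A few women in the primary set will have no MRI, which Section 7.3 already accepts for women who do not tolerate it. The definition should be fixed before the results are seen.
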